6.5. Multicenter Studies

This study will be conducted by multiple investigators at multiple sites internationally. The countries will be categorized into geographic regions, as described in Section [5.2](#).

For the analysis of the primary endpoint, treatment-by-region interaction will be added to the logistic regression model as a sensitivity analysis and results from this model will be compared to the primary model (without the interaction effect). If the treatment-by-region interaction is significant at a 2-sided α level of 0.1, the nature of this interaction will be inspected as to whether it is quantitative (i.e., the treatment effect is consistent in direction across all regions but not in size of treatment effect) or qualitative (the treatment is beneficial in some but not all regions). If the treatment-by-region interaction effect is found to be quantitative, results from the primary model will be presented. If the treatment-by-region interaction effect is found to be qualitative, further inspection will be used to identify in which regions baricitinib is found to be more beneficial.

6.6. Multiple Comparisons/Multiplicity

The primary and key secondary endpoints will be adjusted for multiplicity in order to control the overall family-wise Type I error rate at a 2-sided alpha level of 0.05.

The following is a list of primary and key secondary endpoints to be tested. The subscript for **H** denotes dose (4-mg, 2-mg, 1-mg), the numerical identifier of the endpoint within the dose, and the type of hypothesis (0 for null, 1 for alternative), respectively.

Primary Null Hypotheses:

- **H_{4,1,0}:** Proportion of baricitinib 4-mg patients achieving IGA of 0 or 1 with a ≥ 2 -point improvement from baseline at Week 16 is less than or equal to the proportion of placebo patients achieving IGA of 0 or 1 with a ≥ 2 -point improvement from baseline at Week 16 [IGA0-1]
- **H_{2,1,0}:** Proportion of baricitinib 2-mg patients achieving IGA of 0 or 1 with a ≥ 2 -point improvement from baseline at Week 16 is less than or equal to the proportion of placebo patients achieving IGA of 0 or 1 with a ≥ 2 -point improvement from baseline at Week 16 [IGA0-1]

Key Secondary Null Hypotheses:

- **H_{4,2,0}:** Proportion of baricitinib 4-mg patients achieving EASI75 is less than or equal to the proportion of placebo patients achieving EASI75 at Week 16 [EASI75]
- **H_{4,3,0}:** Proportion of baricitinib 4-mg patients achieving a 4-point improvement in Itch NRS is less than or equal to the proportion of placebo patients achieving a 4-point improvement in Itch NRS at Week 16 [ITCH W16]
- **H_{4,4,0}:** Percent change from baseline in EASI score for baricitinib 4-mg patients is greater than or equal to the percent change from baseline in EASI score for placebo patients at Week 16 [EASI PCFB]
- **H_{4,5,0}:** Proportion of baricitinib 4-mg patients achieving a 4-point improvement in Itch NRS is less than or equal to the proportion of placebo patients achieving a 4-point improvement in Itch NRS at Week 4 [ITCH W4]
- **H_{4,6,0}:** Proportion of baricitinib 4-mg patients achieving SCORAD75 is less than or equal to the proportion of placebo patients achieving SCORAD75 at Week 16 [SCORAD75]
- **H_{4,7,0}:** Proportion of baricitinib 4-mg patients achieving EASI90 is less than or equal to the proportion of placebo patients achieving EASI90 at Week 16 [EASI 90]
- **H_{4,8,0}:** Mean change from baseline in Skin Pain NRS for baricitinib 4-mg patients is greater than or equal to the mean change from baseline in Skin Pain NRS for placebo patients at Week 16 [PAIN W16]
- **H_{4,9,0}:** Mean change from baseline in the score of Item 2 of the ADSS for baricitinib 4-mg patients is greater than or equal to the mean change from baseline in the score of Item 2 of the ADSS for placebo patients at Week 16 [ADSS2 W16]
- **H_{4,10,0}:** Proportion of baricitinib 4-mg patients achieving a 4-point improvement in Itch NRS is less than or equal to the proportion of placebo patients achieving a 4-point improvement in Itch NRS at Week 2 [ITCH W2]
- **H_{4,11,0}:** Mean change from baseline in the score of Item 2 of the ADSS for baricitinib 4-mg patients is greater than or equal to the mean change from baseline in the score of Item 2 of the ADSS for placebo patients at Week 1 [ADSS2 W1]
- **H_{4,12,0}:** Proportion of baricitinib 4-mg patients achieving a 4-point improvement in Itch NRS is less than or equal to the proportion of placebo patients achieving a 4-point improvement in Itch NRS at Week 1 [ITCH W1]
- **H_{2,2,0}:** Proportion of baricitinib 2-mg patients achieving EASI75 is less than or equal to the proportion of placebo patients achieving EASI75 at Week 16 [EASI75]

- **H_{2,3,0}:** Proportion of baricitinib 2-mg patients achieving a 4-point improvement in Itch NRS is less than or equal to the proportion of placebo patients achieving a 4-point improvement in Itch NRS at Week 16 [ITCH W16]
- **H_{2,4,0}:** Percent change from baseline in EASI score for baricitinib 2-mg patients is greater than or equal to the percent change from baseline in EASI score for placebo patients at Week 16 [EASI PCFB]
- **H_{2,5,0}:** Proportion of baricitinib 2-mg patients achieving a 4-point improvement in Itch NRS is less than or equal to the proportion of placebo patients achieving a 4-point improvement in Itch NRS at Week 4 [ITCH W4]
- **H_{2,6,0}:** Proportion of baricitinib 2-mg patients achieving SCORAD75 is less than or equal to the proportion of placebo patients achieving SCORAD75 at Week 16 [SCORAD75]
- **H_{2,7,0}:** Proportion of baricitinib 2-mg patients achieving EASI90 is less than or equal to the proportion of placebo patients achieving EASI90 at Week 16 [EASI90]
- **H_{2,8,0}:** Mean change from baseline in Skin Pain NRS for baricitinib 2-mg patients is greater than or equal to the mean change from baseline in Skin Pain NRS for placebo patients at Week 16 [PAIN W16]
- **H_{2,9,0}:** Mean change from baseline in the score of Item 2 of the ADSS for baricitinib 2-mg patients is greater than or equal to the mean change from baseline in the score of Item 2 of the ADSS for placebo patients at Week 16 [ADSS2 W16]
- **H_{2,10,0}:** Proportion of baricitinib 2-mg patients achieving a 4-point improvement in Itch NRS is less than or equal to the proportion of placebo patients achieving a 4-point improvement in Itch NRS at Week 2 [ITCH W2]
- **H_{2,11,0}:** Mean change from baseline in the score of Item 2 of the ADSS for baricitinib 2-mg patients is greater than or equal to the mean change from baseline in the score of Item 2 of the ADSS for placebo patients at Week 1 [ADSS2 W1]
- **H_{2,12,0}:** Proportion of baricitinib 2-mg patients achieving a 4-point improvement in Itch NRS is less than or equal to the proportion of placebo patients achieving a 4-point improvement in Itch NRS at Week 1 [ITCH W1]
- **H_{1,1,0}:** Proportion of baricitinib 1-mg patients achieving IGA of 0 or 1 with a ≥ 2 -point improvement from baseline at Week 16 is less than or equal to the proportion of placebo patients achieving IGA of 0 or 1 with a ≥ 2 -point improvement from baseline at Week 16 [IGA0-1]
- **H_{1,2,0}:** Proportion of baricitinib 1-mg patients achieving EASI75 is less than or equal to the proportion of placebo patients achieving EASI75 at Week 16 [EASI75]
- **H_{1,3,0}:** Proportion of baricitinib 1-mg patients achieving a 4-point improvement in Itch NRS is less than or equal to the proportion of placebo patients achieving a 4-point improvement in Itch NRS at Week 16 [ITCH W16]
- **H_{1,4,0}:** Percent change from baseline in EASI score for baricitinib 1-mg patients is greater than or equal to the percent change from baseline in EASI score for placebo patients at Week 16 [EASI PCFB]
- **H_{1,5,0}:** Proportion of baricitinib 1-mg patients achieving a 4-point improvement in Itch NRS is less than or equal to the proportion of placebo patients achieving a 4-point improvement in Itch NRS at Week 4 [ITCH W4]
- **H_{1,6,0}:** Proportion of baricitinib 1-mg patients achieving SCORAD75 is less than or equal to the proportion of placebo patients achieving SCORAD75 at Week 16 [SCORAD75]

- **H_{1,7,0}:** Proportion of baricitinib 1-mg patients achieving EASI90 is less than or equal to the proportion of placebo patients achieving EASI90 at Week 16 [EASI90]
- **H_{1,8,0}:** Mean change from baseline in Skin Pain NRS for baricitinib 1-mg patients is greater than or equal to the mean change from baseline in Skin Pain NRS for placebo patients at Week 16 [PAIN W16]
- **H_{1,9,0}:** Mean change from baseline in the score of Item 2 of the ADSS for baricitinib 1-mg patients is greater than or equal to the mean change from baseline in the score of Item 2 of the ADSS for placebo patients at Week 16 [ADSS2 W16]
- **H_{1,10,0}:** Proportion of baricitinib 1-mg patients achieving a 4-point improvement in Itch NRS is less than or equal to the proportion of placebo patients achieving a 4-point improvement in Itch NRS at Week 2 [ITCH W2]
- **H_{1,11,0}:** Mean change from baseline in the score of Item 2 of the ADSS for baricitinib 1-mg patients is greater than or equal to the mean change from baseline in the score of Item 2 of the ADSS for placebo patients at Week 1 [ADSS2 W1]
- **H_{1,12,0}:** Proportion of baricitinib 1-mg patients achieving a 4-point improvement in Itch NRS is less than or equal to the proportion of placebo patients achieving a 4-point improvement in Itch NRS at Week 1 [ITCH W1]

The multiple testing procedure is specified by [Figure JAHL.6.1](#).

[figure not shown]

Figure JAHL.6.1. Illustration of graphical multiple testing procedure with initial α allocation and weights.

The primary null hypotheses includes testing whether neither of baricitinib 4-mg and baricitinib 2-mg dose is superior to placebo at the primary endpoint defined as the proportion of placebo patients achieving IGA of 0 or 1 and ≥ 2 point improvement from baseline at Week 16. The initial alpha allocation is split evenly across these hypothesis to give them “equal footing”, i.e., $H_{4,1,0}$ and $H_{2,1,0}$ will each be first tested at a 2-sided alpha level of 0.025. Together with these primary hypotheses, multiplicity adjusted analyses will be performed on key secondary null hypotheses to control the overall family wise Type I error rate at a 2-sided alpha level of 0.05.

The graphical multiple testing procedure described in Bretz et al. (2011), which is a closed testing procedure will be used; hence it strongly controls the family-wise error rate across all endpoints (Alosh et al. 2014).

If $H_{4,1,0}$ and $H_{2,1,0}$ are not rejected, no further testing is conducted as the α_0 for that test is considered “spent” and cannot be passed to other endpoints. If $H_{4,1,0}$ or $H_{2,1,0}$ is rejected, the testing procedure continues in either branches (starting with $H_{4,2,0}$ and $H_{2,2,0}$ respectively), with α propagated according to the directed edges and propagation weights displayed in [Figure JAHL.6.1](#). Each time a hypothesis is rejected, the graph is updated to reflect the reallocation of α , which is considered “recycled” by Alosh et al. (2014). This iterative process of updating the graph and reallocating α is repeated until all hypotheses have been tested or when no remaining hypotheses can be rejected at their corresponding α levels.

For Japan, the same testing strategy described in the [Figure JAHL.6.1](#) will be used, however, the proportion of patients achieving EASI75 and IGA of 0 or 1 at Week 16 are considered co-primary. Both endpoints have to meet statistical significance compared with placebo with a specific α level based on the graphical multiple testing procedure in order to demonstrate a superiority of a given baricitinib dose (baricitinib 4-mg and/or baricitinib 2-mg) compared with placebo. That is, $H_{4,1,0}$ and $H_{4,2,0}$ have to be rejected in order to demonstrate the superiority of baricitinib 4-mg compared with placebo and $H_{2,1,0}$ and $H_{2,2,0}$ have to be rejected in order to demonstrate the superiority of baricitinib 2-mg compared with placebo.

There will be no adjustment for multiple comparisons for any other analyses.

6.7. Patient Disposition

An overview of patient populations will be summarized by treatment group. Frequency counts and percentages of patients excluded prior to randomization by primary reason for exclusion will be provided for patients who failed to meet study entry requirements during screening.

Patient disposition through Week 16 will be summarized using the ITT population. Frequency counts and percentages of patients who complete the study treatment visits or discontinue early from the study along with whether they completed follow-up, did not complete follow-up or enrolled into the extension will be summarized separately by treatment group for patients who are not rescued and for patients who are rescued, along with their reason for study discontinuation. Frequency counts and percentages of patients who complete the treatment or discontinue treatment early will also be summarized separately by treatment group for patients who are not rescued and for patients who are rescued, along with their reason for treatment discontinuation.

A listing of patient disposition will be provided for all randomized patients, with the extent of their participation in the study and the reason for discontinuation. A listing of all randomized patients with their treatment assignment will also be provided.

6.8. Patient Characteristics

Patient characteristics including demographics and baseline characteristics will be summarized descriptively by treatment group for the ITT population. Historical illnesses and pre-existing conditions will be summarized descriptively by treatment group for the ITT population. No formal statistical comparisons will be made among treatment groups unless otherwise stated.

6.8.1. Demographics

Patient demographics will be summarized as described above. The following demographic information will be included:

- Age
- Age group (<65 vs. \geq 65)
- Age group (<65, \geq 65 to <75, \geq 75 to <85, \geq 85)
- Gender (male, female)
- Race (American Indian or Alaska Native, Asian, Black or African American, Native Hawaiian or Other Pacific Islander, White, Multiple)
- Region (as defined in [Table JAHL.5.1](#))
- Country
- Weight (kg)
- Weight category (<60 kg, \geq 60 to <100 kg, \geq 100 kg)
- Height (cm)
- BMI (kg/m^2)
- BMI category (<25 kg/m^2 , \geq 25 to <30 kg/m^2 , \geq 30 kg/m^2)

A listing of patient demographics will also be provided for the ITT population.

6.8.2. Baseline Disease Characteristics

The following baseline disease information will be categorized and presented for baseline AD clinical characteristics, baseline health outcome measures, and other baseline demographic and disease characteristics as described above:

- Duration since AD diagnosis (years)
- Duration since AD diagnosis category (0 to <2 years, 2 to <5 years, 5 to <10 years, 10 to <20 years, \geq 20 years)
- Age at Diagnosis (years)
- Age Group at Diagnosis (<18 years, \geq 18 to <50 years, \geq 50 years)
- Habits (Alcohol: Never, Current, Former; Tobacco: Never, Current, Former)
- Skin Infections treated with a pharmacological agent within past year (yes, no, unknown; number if yes)
- Atopic Dermatitis Flares within past year (yes, no, unknown; number if yes)
- Validated Investigator's Global Assessment for AD (IGA) score
- Eczema Area and Severity Index (EASI) score
- SCORing Atopic Dermatitis (SCORAD)
- Body Surface Area (BSA) affected by AD
- Hospital Anxiety Depression Scale (HADS) subscales

- Patient-Oriented Eczema Measure (POEM)
- Itch Numerical Rating Scale (NRS)
- Atopic Dermatitis Sleep Scale (ADSS) Item 2
- Dermatology Life Quality Index (DLQI)
- Skin Pain NRS
- Patient Global Impression of Severity (PGI-S-AD)
- Prior therapy (topical therapy only; systemic therapy)
- Prior use of Cyclosporine (yes, no)
- Cyclosporine inadequate response (yes, no)
- Cyclosporine intolerance (yes, no)
- Cyclosporine contraindication [ineligible] (yes, no)
- Cyclosporine inadvisable (yes no)
- Prior use of TCNI (yes, no)
- TCNI inadequate response (yes, no)
- TCNI intolerance (yes, no)
- TCNI contraindication [ineligible] (yes, no)
- TCNI inadvisable (yes, no)
- Vaccine (yes, no)
- Baseline renal function status: impaired ($eGFR < 60 \text{ mL/min/1.73 m}^2$) or not impaired ($eGFR \geq 60 \text{ mL/min/1.73 m}^2$)
- Immunoglobulin E (IgE): intrinsic($< 200 \text{ kU/I}$) or extrinsic ($\geq 200 \text{ kU/I}$)

6.8.3. *Historical Illness and Pre-existing Conditions*

Historical illnesses are defined as those conditions recorded in the Pre-existing Conditions and Medical History electronic case report form (eCRF) or from the Prespecified Medical History: Comorbidities eCRF with an end date prior to the informed consent date. The number and percentage of patients with selected historical diagnoses will be summarized by treatment group using the ITT population. Historical diagnoses will be categorized using the Medical Dictionary for Regulatory Activities (MedDRA®, most current available version) algorithmic standardized MedDRA queries (SMQs) or similar pre-defined lists of preferred terms (PTs) of interest.

Preexisting conditions are defined as those conditions with a start date prior to the first dose of the study drug and stop dates that are at or after the informed consent date or have no stop date (i.e., are ongoing). For events occurring on the day of the first dose of study treatment, the date and time of the onset of the event will both be used to determine if the event was pre-existing. Conditions with a partial or missing start date (or time if needed) will be assumed to be 'not pre-existing' unless there is evidence, through comparison of partial dates, to suggest otherwise. Pre-existing conditions will be categorized using the MedDRA SMQs or similar pre-defined lists of PTs of interest. Frequency counts and percentages of patients with selected pre-existing conditions will be summarized by treatment group using the ITT population.

6.9. *Treatment Compliance*

Patient compliance with study medication will be assessed from Week 0 (Visit 2) to Week 16 (Visit 8) or Early Termination using the ITT population.

All patients are expected to take 3 tablets daily from a blister pack as described in the protocol. Each blister pack contains 27 tablets. A patient is considered noncompliant if he or she misses >20% of the prescribed doses during the study, unless the patient's study drug is withheld by the investigator. For patients who had their treatment temporarily interrupted by the investigator, the period of time that dose was withheld will be taken into account in the compliance calculation.

Compliance in the period of interest up to Visit x will be calculated as follows:

$$\text{Compliance} = \frac{\text{total number of tablets dispensed} - \text{total number of tablets returned}}{\text{expected number of total tablets}}$$

where

- Total number of tablets dispensed: sum of tablets dispensed in the period of interest prior to Visit x ;
- Total number of tablets returned: sum of the tablets returned in the period of interest prior to and including Visit x ;
- Expected number of tablets: number of days in the period of interest*number of tablets taken per day = [(date of last dose – date of first dose + 1) – number of days of temporary drug interruption]*number of tablets taken per day

Patients who are significantly noncompliant (compliance <80%) through Week 16 will be excluded from the PPS population.

Descriptive statistics for percent compliance and non-compliance rate will be summarized for the ITT population by treatment group for Week 0 through Week 16. Sub-intervals of interest, such as compliance between visits, may also be presented. The number of expected doses, tablets dispensed, tablets returned, and percent compliance will be listed by patient for Week 0 through Week 16.

6.9.1. Rescue Treatment

Descriptive statistics for drug accountability of topical low and moderate potency rescue medication provided by the sponsor will also be supplied, including the amount utilized throughout the treatment period. The total amount in grams for low and moderate potency will be summarized between scheduled visits as well as throughout the entire 16 week treatment period.

The dispensed weight of sponsor-provided TCS tubes for the two different potencies (low and moderate) varies between countries due to different supply regions. Average weights of full tubes were used to determine the dispensed weights for each region. Returned tubes were weighed with cap (without the carton) to determine the amount of TCS in grams (g) used at each visit.

For low potency TCS, the dispensed tube weight with cap (without the carton) in Japan is 13.5g. For countries supplied by European distributors (Czech Republic, Denmark, France, Germany, Italy, and Russia), the dispensed weight of low potency TCS is 21g. The remaining countries, supplied by US distributors (India, Mexico, and Taiwan), the weight of low potency TCS is 40 g.

For moderate potency TCS, the dispensed tube weight with cap (without the carton) in Japan is 13.5g. For countries supplied by European distributors, the dispensed weight of moderate potency TCS is 38g. The remaining countries, supplied by US distributors, the weight of moderate potency TCS is 40g.

If a returned tube is not weighed or not returned then the tube can be classified as partially used, fully used, unused, or unknown. Partially used rescue medication tubes will be defined as 50% used whereas fully used and unused tubes will be defined as 100% and 0% used respectively. When drug accountability is not performed for a particular tube of rescue medication or an answer of 'unknown' is given for a tube which is not returned, that particular tube will not be included in the analysis.

The number of days rescue therapy is used for each patient is also collected on the diary device. The proportion of time that the patients did not use rescue therapy will be summarized for the aforementioned visit intervals by potency (low or moderate) and both potencies combined. For this analysis, the date of the first entry on the diary device will be used to signify the first day of rescue therapy use.

Additionally, a summary of the initial rescue therapy and the reason for requiring initial rescue will be produced, as well as a summary of the proportion of patients rescued at each study visit. A summary of all rescue medications will be provided.

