4.3. Exploratory Objectives

The exploratory objectives of this study are the following:

Objectives/Endpoints

• Mean change from baseline in nocturnal itch assessed by actigraphy device at 1 week and 4 weeks• Frequency of patient-reported “no itch” (Itch NRS score = 0) days from daily diaries from Week 12 to Week 16• Frequency of patient-reported “no pain” (Skin Pain NRS score = 0) days from daily diaries from Week 12 to Week 16• Mean change from baseline in the score of Item 1 of the ADSS at 1 week and 16 weeks• Mean change from baseline in the score of Item 3 of the ADSS at 1 week and 16 weeks• To evaluate changes from baseline in immunoglobulin E levels during the study• To evaluate changes from baseline in eosinophil levels during the study• To characterize baricitinib pharmacokinetics in the AD population and explore relationships between baricitinib exposure and study endpoints• To assess time to 4-pt itch reduction during the first 14 days after initiation of treatment• To assess time to improvement in Skin Pain during the first 14 days after the initiation of treatment• To assess the use of rescue therapy through the weight of sponsor provided topical corticosteroid and number of days not using rescue therapy

5. Study Design

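### Rescue-steroid tubes with unknown use are left out of a summed gram total, so they count as 0 g used and the total can only be right or too low

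*SAP*

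**What the plan says.** The measure comes from the last exploratory objective in SAP Section 4.3: "To assess the use of rescue therapy through the weight of sponsor provided topical corticosteroid and number of days not using rescue therapy". SAP Section 6.9.1 makes it a total in grams for low and moderate potency, which "will be summarized between scheduled visits as well as throughout the entire 16 week treatment period".

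Grams used come from weighing returned tubes against a fixed dispensed weight for each supply region. The stated weights include the cap and exclude the carton. For European supply, "the dispensed weight of low potency TCS is 21g" and, for the other product, "For countries supplied by European distributors, the dispensed weight of moderate potency TCS is 38g". Tubes for Japan are 13.5 g and US-supplied tubes are 40 g, for both potencies.

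A tube that was not weighed or not returned can be classed in one of four ways. Three have a value: "Partially used rescue medication tubes will be defined as 50% used whereas fully used and unused tubes will be defined as 100% and 0% used". The fourth class is unknown. If the answer is unknown for a tube not returned, or if accountability was not done, "that particular tube will not be included in the analysis".

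The section does not say what total a patient receives when every tube is unknown. It gives no sensitivity analysis for excluded tubes and does not commit to reporting how many there were.

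**The concern.** In a mean, dropping an unknown item leaves an average of the rest. In a sum, dropping it sets it to zero. Section 6.9.1 separates unknown from unused, and its exclusion rule then gives both the same contribution. The error has one direction: the total is correct only if every excluded tube was in fact unused.

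Zero is a weak default here. Under footnote h of the protocol's Schedule of Activities, rescue steroid is dispensed and weighed only for patients who met rescue criteria. Protocol Section 7.7.3 reserves rescue for unacceptable or worsening symptoms.

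The SAP is more careful with comparable quantities. In Table JAHL.6.6, a count of itch-free or pain-free days is missing if the four-week interval has fewer than 16 assessments. In Section 6.2.2, a weekly diary mean is missing with fewer than 4 values. The gram total has no such rule.

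At stake is the accuracy of the only planned measure of the quantity of rescue steroid. A reader of the report also could not tell how many tubes had been left out.

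**Working it through.** The documents state no gram total, no share of unknown tubes and no rescue rate by arm, so there is no planned figure to reproduce. Only the tube weights below come from the SAP; every other input is an assumption.

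**One tube.** Let *w* be the dispensed weight and *f*ᵤ the true share used. The rule records 0 g, so the shortfall is *w* × *f*ᵤ. This runs from 0 g to *w*, that is, to at most 13.5 g (Japan), 21 g (European low potency), 38 g (European moderate potency) or 40 g (US supply). Because these weights include the packaging, the true ceiling is the contents, which is somewhat less.

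**One patient.** Take four European moderate-potency tubes, three fully used and one unknown. The reported total is 3 × 38 = 114 g.

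| Unknown tube in truth | True total | Shortfall |
|---|---|---|
| 0% used | 114 g | 0 g |
| 50% used | 114 + 19 = 133 g | 19 g (14.3%) |
| 100% used | 114 + 38 = 152 g | 38 g (25%) |

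**Two arms, equal unknown rate.** Assume *w* = 38 g, an average of 70% used in known and unknown tubes alike, and 4 tubes per patient in a high-rescue arm against 2 in a low-rescue arm. True means are 4 × 38 × 0.7 = 106.4 g and 2 × 38 × 0.7 = 53.2 g, a difference of 53.2 g and a ratio of 2.0. With a share *u* of tubes unknown in both arms, each mean is multiplied by (1 − *u*).

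| *u* | High arm | Low arm | Difference | Ratio |
|---|---|---|---|---|
| 5% | 101.1 g | 50.5 g | 53.2 × 0.95 = 50.5 g | 2.0 |
| 10% | 95.8 g | 47.9 g | 53.2 × 0.90 = 47.9 g | 2.0 |
| 20% | 85.1 g | 42.6 g | 53.2 × 0.80 = 42.6 g | 2.0 |

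The high-rescue arm loses more grams, but both arms lose the same percentage. If unknown tubes are not used like known ones, the relative shortfall at *u* = 10% runs from 0% (all unused) to 15.2 / (95.8 + 15.2) = 13.7% (all fully used), where 15.2 = 4 × 38 × 0.1.

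**Two arms, unequal unknown rates.** The reported difference is 106.4 × (1 − *u*high) − 53.2 × (1 − *u*low).

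- 20% high, 5% low: 85.1 − 50.5 = 34.6 g, narrower than the true 53.2 g.
- 5% high, 10% low: 101.1 − 47.9 = 53.2 g, unchanged, because both arms lose 5.3 g.
- 5% high, 20% low: 101.1 − 42.6 = 58.5 g, wider than the truth. The shortfalls are 5.3 g and 10.6 g.

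So the sign of the bias in the arm difference depends on rates that the documents do not give.

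**The case against.** The strongest reply is that little depends on this. Section 6.9.1 is a descriptive accountability summary for one exploratory objective. It does not appear in Tables JAHL.6.5 or JAHL.6.7, and no test of grams is planned. The primary and key secondary analyses use the fact of rescue, through the censoring rules in SAP Section 6.4, and never the amount. Other descriptions do not need returned tubes: diary days of rescue use, the proportion rescued at each visit, and a summary of all rescue medications. All of this stands and sets the low severity.

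A second reply is that a dispensed tube need not have been used. Protocol Section 7.7.3 allows two products together and recommends the low-potency one for stepping down, so some unknown tubes may be unopened. This also stands. It is why the shortfall starts at 0 g and why imputation at the mean needs bounds beside it. It does not justify fixing every unknown tube at the lower bound.

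A third reply is that the zero is not settled for a patient whose tubes are all unknown, since the SAP could mean either 0 g or missing. That is correct, and it is a further gap to close.

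**Conclusion.** The point holds as a minor one. For any patient with at least one counted tube, Section 6.9.1 scores an unknown tube as unused, and the total is either correct or too low by up to the contents of each such tube. This follows from the stated rule alone. Its effect on an arm's total cannot be sized from the documents; the arm figures above rest on assumed tube counts, usage and unknown rates.

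Two stronger readings are tempting, and the documents do not support them.

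- A reader might infer that placebo use is understated most and that the arm comparison is therefore pulled towards no difference. In grams this follows if unknown rates and usage per tube are similar across arms, given more rescue on placebo. The ratio is then unaffected, and a sufficiently higher unknown rate on baricitinib would widen the difference instead. No rate by arm is given.
- A reader might infer that 16-week totals are also too low for patients who leave early. Section 6.9.1 describes the amount used during the treatment period, and for an early leaver the sum is a correct record of that. Use had the patient stayed is a different quantity. The protocol also provides for weighing returned tubes at the early termination visit and at Visit 801.

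**What to change.** In SAP Section 6.9.1, replace the exclusion rule with the following:

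1. Impute a tube with no accountability or unknown use at the mean grams used per accounted tube of the same potency and supply region.
2. Beside that result, show the totals with these tubes set to 0%, 50% and 100% used. For patients with at least one counted tube, the 0% version reproduces the present rule.
3. For a patient whose tubes are all unknown, set the total to missing, not 0 g, before imputation. State that the same applies within a potency and visit interval.
4. Report the number and share of unaccounted tubes by treatment arm.

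The cost is a few lines of SAP text and a small change to one derivation. No new data are needed and no confirmatory analysis changes. The downside is one simple imputation assumption, which the bounds make visible.
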